Duration of Participation	
Each participant will participate in the study for approximately 6 years from the time the participant provides documented informed consent through the final contact. After a screening phase of 28 days, each participant will be receiving assigned intervention to 17 administrations (approximately 1 year). After the end of treatment, each participant will be followed for 30 days for AEs. Serious adverse events will be collected for 90 days after the end of treatment or for 30 days after the end of treatment if the participant initiates new anticancer therapy, whichever is earlier.
 
Each participant will participate in the study from the time that the participant provides documented informed consent through the final protocol-specified contact.
 
After a screening phase, each participant will be assigned to receive study intervention (pembrolizumab or placebo) until disease recurrence is documented by investigator and verified by BICR, unacceptable adverse event(s) (AEs), intercurrent illness that prevents further administration of treatment, investigator's decision to discontinue the participant, administrative reasons requiring cessation of treatment, or until the participant has received 17 administrations of pembrolizumab or placebo (approximately 1 year).
 
Disease recurrence will be documented by investigator radiographically (with site radiologist) and will be verified by BICR. Disease recurrence will be verified by BICR prior to DC of study intervention. No cross-over is allowed in this study. For participants who DC for reasons other than BICR-verified disease recurrence or BICR-verified intra-hepatic recurrence, imaging should continue to be performed as if on study until extra-hepatic disease recurrence has been verified by BICR. Disease recurrence can also be confirmed with pathology if required per the site's standard of care.
 
After the end of study treatment, each participant will be followed for the occurrence of AEs and spontaneously reported pregnancy as described under Section 8.4.4.
 
Participants who initiate a new non-study cancer treatment should continue to have post-treatment distant metastases-free survival (DMFS) follow-up until extra-hepatic disease recurrence is documented by investigator (radiographically and/or with subsequent pathology) and verified by BICR.
 
All participants will be followed for overall survival until death, withdrawal of consent, or the end of the study.

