Investigators will assess disease recurrence radiographically (with site radiologist) during study intervention and efficacy follow-up. Disease recurrence will be documented by the investigator radiographically (with site radiologist) and will be verified by BICR prior to discontinuation of study intervention. Disease recurrence can also be confirmed with pathology if required per the site's standard of care. For participants who discontinue for reasons other than BICR-verified extrahepatic disease recurrence or confirmed with pathology if required per the site's standard of care, imaging should continue to be performed as if on study intervention until extrahepatic disease recurrence has either been verified by BICR or confirmed with pathology if required per the site's standard of care.

Disease recurrence can be intrahepatic or extrahepatic:

- Intrahepatic disease recurrence will be defined as the appearance of one or more intrahepatic lesions with a longest diameter of at least 10 mm and a typical vascular pattern of HCC on triphasic CT scan or MRI of the abdomen (ie, hypervascularization in the arterial phase with washout in the portal venous or late venous phase). Intrahepatic lesions larger than 10 mm that do not show a typical vascular pattern may be diagnosed as HCC by evidence of a growth interval of at least 10 mm in ≥ 4 weeks after the initial scan showing disease recurrence. Both de novo liver tumors and intrahepatic metastases will be considered intrahepatic disease recurrence.

- Extrahepatic disease recurrence will be defined as the appearance of one or more unequivocal new extra-nodal lesions or malignant enlargement of a previously normal lymph node. If a potential new extra-nodal lesion is equivocal, for example because of small size or clinical presentation, continued follow-up will show whether it truly represents disease recurrence. If it is later confirmed as disease recurrence, it should be retrospectively assigned at the visit where it was first seen. A lymph node ≥ 15 mm in short axis is presumed to represent disease recurrence. A lymph node 10-14 mm in short axis may represent disease recurrence, with reviewers using additional information (such as location, morphological signs and change in size) to inform their clinical judgment to determine whether it represents disease recurrence. Participants will also be discontinued from study intervention if they have ascites or pleural effusion deemed to be malignant.

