8.2 Efficacy/Immunogenicity Assessments

8.2.1 Tumor Imaging and Assessment of Disease

In addition to survival, efficacy will be assessed based on imaging evaluation of changes in tumor burden over time, until the participant is discontinued from the study or goes into survival follow-up. The process for image collection and transmission to the iCRO can be found in the Site Imaging Manual (SIM). Tumor imaging is strongly preferred to be acquired by CT. For the abdomen and pelvis, contrast-enhanced MRI may be used when CT with iodinated contrast is contraindicated, or when mandated by local practice. Magnetic resonance imaging is the strongly preferred modality for imaging the brain, if clinically indicated. The same imaging technique should be used in a participant throughout the study to optimize the reproducibility of the assessment of existing and new tumor burden and improve the accuracy of the response assessment based on imaging.

Note: for the purposes of assessing tumor imaging, the term “investigator” refers to the local investigator at the site and/or the radiological reviewer at the site or at an offsite facility.

All scheduled images for all study participants from the sites will be submitted to the iCRO. In addition, images (including via other modalities) that are obtained at an unscheduled time point to determine disease recurrence, as well as imaging obtained for other reasons, but which show radiologic recurrence, should also be submitted to the iCRO. After the investigator determines absence of radiologic disease, expedited verification of absence of radiologic evidence of disease will be performed by BICR at Screening and will be used to determine participant eligibility.

When the investigator identifies radiographic recurrence, the iCRO will perform expedited verification of radiologic recurrence by BICR and communicate the results to the study site and Sponsor via email. Imaging should continue until disease recurrence has been verified by BICR (see Section 8.2.1.2). All scans must be submitted to the iCRO until extrahepatic disease recurrence has been verified by BICR. Once extrahepatic disease recurrence has been verified centrally, subsequent imaging (if acquired) should not be submitted to the iCRO.

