Participants should continue treatment or continue in the Efficacy Follow-up Phase until disease recurrence has been verified by BICR or confirmed with pathology if required per the site’s standard of care. Exceptionally, if the investigator identifies disease recurrence that is not verified by BICR and the participant is clinically unstable or unable to continue study intervention due to rapid clinical deterioration, study intervention or continue in the Efficacy Follow-up Phase may be discontinued after consultation with the Sponsor.

Clinical instability is defined as the following:

- Symptoms and signs indicating clinically significant progression of disease
- Decline in ECOG performance status

- Requirements for intensified management, including increased analgesia, radiation or other palliative care

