8.2.1.3 End-of-Treatment and Follow-up Tumor Imaging

For participants who discontinue study intervention, tumor imaging should be performed at the time of treatment discontinuation (± 4 week window). If previous imaging was obtained within 4 weeks prior to the date of discontinuation, then imaging at treatment discontinuation is not mandatory.

For participants who DC study intervention for reasons other than BICR-verified disease recurrence or BICR-verified intra-hepatic recurrence, imaging should continue to be performed as if on study (see Sec. 8.2.1.2) until extra-hepatic disease recurrence is verified by BICR, pregnancy, death, withdrawal of consent, or the end of the study, whichever occurs first.

NOTE: Participants who do not have confirmed extrahepatic recurrence, but decline study-specific imaging in Efficacy Follow-Up and move to Survival-Follow Up Phase, should be encouraged to submit imaging performed as standard of care (even retrospectively) in the Survival-Follow Up Phase.

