8.2.2 Patient-reported Outcomes

The EQ-5D-5L and EORTC QLQ-C30, and EORTC QLQ-HCC18 questionnaires will be administered by trained site personnel and completed by participants in the following order: EQ-5D-5L first, then EORTC QLQ-C30, then EORTC QLQ-HCC18. The questionnaires should be administered prior to dosing on Day 1 of each cycle from Cycle 1-10 both inclusive, then on Day 1 of Cycle 12, 14, 16, at EOT, and at the 30-day Safety Follow-up Visit. For participants who discontinue from study intervention prior to Cycle 17, PROs will be collected Q12W from the EOT Visit during the remainder of Year 1. After Year 1, PROs are to be performed Q24W to align with imaging visits. After Year 2, PROs are to be performed Q24W to align with imaging visits, up to and including Week 216. PROs are collected again at Week 228, and Week 252 PROs should be collected up to and including Year 5 (Week 252).

It is best practice and strongly recommended that patient-reported outcomes (PROs) are administered to randomized participants prior to drug administration, AE evaluation, and disease status notification. If the participant does not complete the PROs at a scheduled time point, the MISS_MODE form must be completed to capture the reason the assessment was not performed.

NOTE: For some sites, the translated EORTC QLQ-C30 and/or EORTC QLQ-HCC18 might become available after study startup and should be administered to participants at their time of enrollment; for some sites, the EORTC QLQ-C30 and/or EORTC QLQ-HCC18 translation might not be available for the entire duration of the study.

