8.11.2.2 Efficacy Follow-up Visits

Participants who complete the protocol-required cycles of study intervention or who discontinue study intervention for a reason other than BICR-verified extrahepatic disease recurrence will move into the Efficacy Follow-up Phase and tumor imaging should continue to be performed as if on study intervention (see Section 8.2.1.2), until extrahepatic disease recurrence is documented radiographically by the investigator (with site radiologist) and verified by BICR. Pathology may also be used to confirm disease recurrence if required per the site's standard of care.

Every effort should be made to collect information regarding disease status, the start of new anticancer therapy, disease recurrence, death or end of study. Information regarding poststudy anticancer treatment will be collected if new treatment is initiated.

Participants who completed all efficacy assessments and/or will not have further efficacy assessments must enter the Follow-up Phase.

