8.11.2.3 Survival Follow-up Contacts

Participant survival follow-up status will be assessed approximately every 12 weeks until death, withdrawal of consent, or the end of the study, whichever occurs first. Participants with initial recurrence as intrahepatic recurrence will continue imaging as detailed in Sections 8.2.1.1 and 8.2.1.2 and efficacy follow-up until extrahepatic disease recurrence after which they will move into the Survival Follow-up Phase.

The first survival follow-up contact should be scheduled as described below:

- For participants who discontinue treatment intervention and who will not enter the Efficacy Follow-up Phase, the first survival follow-up contact will be scheduled 12 weeks after the Discontinuation Visit and/or Safety Follow-up Visit (whichever is last).
- For participants who completed assessments in the Efficacy Follow-up Phase, the first survival follow-up contact will be scheduled 12 weeks after the last Efficacy Assessment Follow-up Visit has been performed.

8.11.3 Participants Discontinued from Study Intervention but Continuing to be Monitored in the Study

Participants who discontinue study intervention prior to completion of the planned treatment regimen should be encouraged to continue to be followed for all remaining study visits.

When a subject discontinues/withdraws from participation in the trial, all applicable activities scheduled for the final visit should be performed at the time of discontinuation. Any adverse events that are present at the time of discontinuation/withdrawal should be followed in accordance with the safety requirements outlined in Section 10.3.5– Recording AE and SAE.

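### After a BICR-verified intrahepatic first recurrence, the protocol words the end of Efficacy Follow-up and imaging inconsistently, which puts later PRO and metastasis data at risk

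*Combined protocol and SAP*

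**What the plan says.** Consider a participant whose first recurrence is intrahepatic and verified by BICR.

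**Wording that points to a stop at any recurrence**
- Section 8.2.1: "Participants should continue treatment or continue in the Efficacy Follow-up Phase until disease recurrence has been verified by BICR" (or confirmed by pathology). An earlier sentence in the same section also ends imaging at verified recurrence without naming the site of disease, though it refers the reader to 8.2.1.2.
- Section 8.2.1.3: "For participants who DC study intervention for reasons other than BICR-verified disease recurrence or BICR-verified intra-hepatic recurrence, imaging should continue". The synopsis has nearly the same sentence: "For participants who DC for reasons other than BICR-verified disease recurrence or BICR-verified intra-hepatic recurrence, imaging should continue to be performed".

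**Wording that continues to extrahepatic recurrence**
- Section 4.1 continues imaging "For participants who discontinue for reasons other than BICR-verified extrahepatic disease recurrence" or pathology confirmation.
- Section 8.2.1, directly after its unqualified imaging sentence, requires scans to be sent to the imaging CRO until extrahepatic recurrence is verified.
- Section 8.2.1.2 sets a specific imaging schedule after intrahepatic recurrence: every 24 weeks to about Year 5, then annually to about Year 7.
- Section 8.11.2.2: participants who complete treatment or "discontinue study intervention for a reason other than BICR-verified extrahepatic disease recurrence will move into the Efficacy Follow-up Phase".
- Section 8.11.2.3: "Participants with initial recurrence as intrahepatic recurrence will continue imaging as detailed in Sections 8.2.1.1 and 8.2.1.2 and efficacy follow-up until extrahepatic disease recurrence", and only then move to Survival Follow-up.

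**PROs.** Section 8.2.2 states: "After Year 1, PROs are to be performed Q24W to align with imaging visits". Collection runs to Week 252. The Schedule of Activities shows the later PROs under the Efficacy Follow-up columns.

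**The concern.** Section 8.2.1 is the parent imaging section, and 8.2.1.3 is where a site would look for a participant who has stopped treatment. A site could reasonably rely on either. On the shorter reading, the participant leaves Efficacy Follow-up at the first intrahepatic recurrence. Nothing then says explicitly that PROs go on outside that phase.

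The secondary PRO endpoints in Section 9.4.3 are change from baseline and time to confirmed deterioration (TTD). TTD needs a deterioration to be confirmed at the next visit, so one first seen at the last visit before exit could not be confirmed. Recurrence is what the treatment is meant to delay. If follow-up stops there, missingness is tied to an outcome that may differ by arm and may itself affect quality of life. Follow-up for distant metastases, which the synopsis continues to extrahepatic recurrence, would be cut in the same way. PRO assessments that are missed cannot be recovered later.

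**Working it through.** **Step 1. Put the rules side by side.** No stated figure in the plan bears on this point, so the finding rests on the text.

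| Section | End of imaging or efficacy follow-up after intrahepatic recurrence |
|---|---|
| 8.2.1, efficacy follow-up sentence | any verified recurrence |
| 8.2.1, first imaging sentence | any verified recurrence, with a reference to 8.2.1.2 |
| 8.2.1, next sentence (scan submission) | extrahepatic recurrence |
| 8.2.1.3 and synopsis | ambiguous: the exception may exclude or include these participants |
| 4.1, 8.2.1.2, 8.11.2.2, 8.11.2.3 | extrahepatic recurrence |

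The 8.2.1 sentence governs treatment and follow-up together. Its treatment half agrees with Section 7.1, where recurrence at either site ends study intervention. Only the follow-up half conflicts with the other sections.

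**Step 2. How many participants could meet the disputed rule.**
- Inputs: control RFS median 33.8 months (Section 9.9.1); 475 per arm (Section 9.9.2).
- Assumptions: exponential RFS, no censoring. The share of first events that are intrahepatic is not in the documents and is taken as 50%, 70% or 90%.
- F(t) = 1 − exp(−ln 2 × t / 33.8)
- F(12) = 0.218, F(36) = 0.522, F(60) = 0.708
- By 60 months: 475 × 0.708 ≈ 336 control participants with an RFS event. Multiplied by 0.5, 0.7 and 0.9, this gives about 168, 235 and 303.

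**Step 3. Share of later PRO visits that fall after such a recurrence.** Assume visits at Weeks 72, 96, 120, 144, 168, 192, 216, 228 and 252, which is the 24-week pattern to Week 216 plus the two named later weeks. Convert with months = weeks × 7 / 30.4375.

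| Week | 72 | 96 | 120 | 144 | 168 | 192 | 216 | 228 | 252 |
|---|---|---|---|---|---|---|---|---|---|
| F | 0.288 | 0.364 | 0.432 | 0.493 | 0.547 | 0.596 | 0.639 | 0.659 | 0.695 |

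The sum is 4.713, and the mean is 4.713 / 9 = 0.524. Multiplying by the assumed share gives 0.26 at 50%, 0.37 at 70% and 0.47 at 90%.

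This ignores deaths. It also counts visits after a later extrahepatic recurrence, when imaging ends under both readings. It is therefore an upper bound on what the wording puts at risk.

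**Step 4. Two single-participant examples, on the same visit grid.**
- Recurrence on treatment at Week 36, follow-up continuing: end of treatment, 30-day visit, one 12-weekly visit in Year 1 and nine later visits, 12 in all. If Efficacy Follow-up ends at recurrence, the end-of-treatment and 30-day visits remain. So does the Year 1 visit if 8.2.2 is followed as written. That makes 2 or 3.
- Recurrence off treatment at Week 96: 7 further visits if follow-up continues, and none if a site ends PROs with the phase.

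**The case against.** The two readings are not equally supported. The 8.2.1 sentence mainly tells sites not to stop before BICR verification, and it leads into the exception for unverified recurrence in unstable participants. The sections that deal with intrahepatic recurrence specifically all continue to extrahepatic recurrence. In 8.2.1.3 and the synopsis, the separate mention of intrahepatic recurrence would be redundant if the phrase were meant to exclude those participants. The 8.2.1.3 sentence also refers to 8.2.1.2 and itself ends at extrahepatic recurrence. Section 7.1 lists recurrence as a reason to stop treatment while staying monitored, and says that all Schedule of Activities visits should be completed. All of this stands. It shows the likely intent, but it does not remove the conflicting words from the sections that a site would consult.

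A reader might infer that the wording decides whether all post-recurrence PRO and metastasis data exist. The documents do not support that:
- The end-of-treatment, 30-day and Year 1 12-weekly PROs have no recurrence condition, and PROs are stated to Year 5.
- Follow-up for distant metastasis-free survival has its own extrahepatic stop in the synopsis. That measure is not a listed primary or secondary endpoint in the visible text; the exploratory endpoints are redacted.
- Standard-of-care scans may be submitted during Survival Follow-up.

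A reader might also infer a definite bias in the TTD hazard ratio. The documents give no deterioration rate before or after recurrence, so neither direction nor size can be derived. The time point for change from baseline is still to be set by blinded review, PROs carry no formal hypothesis, and details are left to the supplemental SAP.

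**Conclusion.** The inconsistency is real, in current operational text, and should be corrected. It is a moderate wording problem, not a demonstrated loss of data. The balance of the text favors continuing to extrahepatic recurrence. The risk is that some sites act on 8.2.1, or on the excluding reading of 8.2.1.3 and the synopsis, and end imaging and the PRO visits aligned with it at first recurrence. That loss would be potentially informative for the secondary PRO endpoints and for metastasis follow-up.

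The 26-47% figure for control-arm PRO visits between Weeks 72 and 252 shows scale only. It rests on exponential RFS, an assumed intrahepatic share and no deaths, and it would apply only if every site used the shorter rule. The primary endpoints do not depend on this point: the RFS event is fixed at first recurrence, and survival is followed in either phase.

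**What to change.** Reconcile the sections to one follow-up stop rule.

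- **Section 8.2.1:** separate the efficacy follow-up and imaging clause from the treatment clause. Leave the treatment clause unchanged. Align the follow-up clause, and the unqualified imaging sentence before it, with 8.2.1.2, 8.11.2.2 and 8.11.2.3: until extrahepatic recurrence is BICR-verified or confirmed by pathology.
- **Section 8.2.1.3 and synopsis:** reword the exception so that participants with BICR-verified intrahepatic recurrence are plainly included in continued imaging under 8.2.1.2.
- **Section 8.2.2:** state that PROs continue at those visits after intrahepatic recurrence, through Week 252.

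The cost is protocol wording and a letter to sites. No visits are added, because the specific sections already require them.

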8.2.1.2 Tumor Imaging During the Study

The first on study imaging assessment should be performed at 12 weeks (± 7 days) from the date of randomization. Imaging should be performed Q12W until Week 228 (± 14 days) (~Year 4), Q24W thereafter until Week 260 (± 14 days) (~Year 5), and annually thereafter for up to 2 years (~Year 7) or until any initial recurrence (intrahepatic or extrahepatic), whichever occurs first. Follow the schedule below after initial recurrence based on intra-hepatic or extra-hepatic recurrence. Recurrence should be BICR-verified or confirmed with pathology if required per the site's standard of care.

- If BICR-verified intrahepatic recurrence with absence of extra-hepatic recurrence, tumor imaging should be performed Q24W thereafter until Week 260 (± 14 days) (~Year 5), and annually thereafter for up to 2 years (~Year 7), until extra-hepatic disease recurrence is documented radiographically by the investigator (with site radiologist) and verified by BICR. Disease recurrence can also be confirmed with pathology if required per the site's standard of care.
- Imaging should be discontinued after extra-hepatic recurrence that is verified by BICR. Disease recurrence can also be confirmed with pathology if required per the site's standard of care.

Imaging timing should follow calendar days from randomization and should not be adjusted for delays in cycle starts. Imaging should continue to be performed until extra-hepatic disease recurrence is identified by the Investigator and verified by BICR or confirmed with pathology if required per the site's standard of care, withdrawal of consent, death, or notification by the Sponsor, whichever occurs first.

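### The unstable-participant exception in Section 8.2.1 joins stopping treatment to stopping RFS imaging and is not reconciled with Sections 8.11.2.2, 8.2.1.3 and 4.1

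*Combined protocol and SAP*

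**What the plan says.** Section 8.2.1 first sets a general rule: participants stay on treatment or in Efficacy Follow-up until recurrence is verified by BICR or, where site practice requires it, confirmed by pathology. It then makes an exception: "Exceptionally, if the investigator identifies disease recurrence that is not verified by BICR and the participant is clinically unstable", or unable to continue study intervention because of rapid clinical deterioration, "study intervention or continue in the Efficacy Follow-up Phase may be discontinued after consultation with the Sponsor". Clinical instability is defined by a short list that includes "Symptoms and signs indicating clinically significant progression of disease" and "Decline in ECOG performance status".

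Section 8.11.2.2 says that participants "who discontinue study intervention for a reason other than BICR-verified extrahepatic disease recurrence will move into the Efficacy Follow-up Phase", and that "tumor imaging should continue to be performed as if on study intervention (see Section 8.2.1.2), until extrahepatic disease recurrence is documented radiographically by the investigator" and verified by BICR. Sections 4.1 and 8.2.1.3 follow the same principle. Section 8.2.1.2 says "Imaging should continue to be performed until extra-hepatic disease recurrence is identified by the Investigator and verified by BICR" or confirmed by pathology, but it also lists withdrawal of consent, death and notification by the Sponsor as stopping points. None of these sections refers to the exception in 8.2.1.

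The primary RFS event (9.4.1) is recurrence by BICR or pathology, or death from any cause. Section 9.6.1.1 counts recurrences whether or not study intervention has been discontinued.

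**The concern.** Being too unwell to continue study intervention is a reason to consider stopping treatment. It is not in itself a reason to end follow-up for the primary endpoint, yet the sentence allows either. A participant who leaves Efficacy Follow-up this way goes to survival contacts with a suspected recurrence that has not become an RFS event.

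A later scan may be exactly what BICR needs. Under 4.1, an intrahepatic lesion without the typical vascular pattern can be diagnosed by growth of at least 10 mm over at least 4 weeks. An equivocal extra-nodal lesion is settled by continued follow-up and then dated back to the visit where it was first seen. Without that scan, the event may be missed or appear only at death.

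Because instability includes signs of progression, leaving is related to the endpoint. RFS carries the trial: success is defined on it, and OS is tested only if the RFS null hypothesis is rejected (4.2).

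**Working it through.** **Text comparison**

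| Section | What ends endpoint imaging | Mentions the exception? |
|---|---|---|
| 8.2.1, exception | Unverified investigator-called recurrence, plus instability or rapid deterioration, plus Sponsor consultation | It is the exception |
| 8.11.2.2 | BICR-verified extrahepatic recurrence (pathology allowed) | No |
| 8.2.1.3 | BICR-verified extrahepatic recurrence, pregnancy, death, consent withdrawal, end of study | No |
| 4.1 | BICR-verified or pathology-confirmed extrahepatic recurrence | No |
| 8.2.1.2 | Verified extrahepatic recurrence, consent withdrawal, death, Sponsor notification | No |

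Section 8.2.1 requires all scans to go to the imaging CRO until extrahepatic recurrence is verified. The same section says imaging-based efficacy assessment runs until the participant enters survival follow-up, so it is unclear whether the submission rule survives an exit by the exception. The NOTE in 8.2.1.3 only encourages submission of standard-of-care scans at that stage, and it addresses participants who decline study imaging.

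**Size (illustration only)**

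The documents show no RFS hazard ratio, alpha, power, event count or analysis time, so there is no design figure to reproduce.

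- From 9.9.1: 950 participants at 1:1 (475 per arm), control median RFS 33.8 months, 36-month enrollment.
- Assumed: exponential RFS, uniform enrollment, no dropout, two-sided alpha 0.05, HR 0.70 to 0.80, analysis at T = 48 to 72 months.

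The probability of an event by T is P = 1 − [exp(−λ(T−36)) − exp(−λT)]/(36λ). At HR 0.75 and T = 60:

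- Placebo: λ = ln 2/33.8 = 0.0205, P = 0.568.
- Pembrolizumab: λ = 0.75 × 0.0205 = 0.0154, P = 0.469.
- Expected events: 475 × (0.568 + 0.469) ≈ 493.

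Power (Schoenfeld) = Φ(|ln HR|·√D/2 − 1.96). With D = 493 this is Φ(0.2877 × 22.20/2 − 1.96) = Φ(1.23) = 0.891.

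| Events lost, equal in both arms | Events left | Power |
|---|---|---|
| 1% | 488 | 0.888 |
| 3% | 478 | 0.882 |
| 5% | 468 | 0.875 |
| 10% | 443 | 0.857 |

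Over the whole assumed grid, a 5% loss costs between 0.3 points (HR 0.70, T = 72: 0.989 to 0.986) and 2.2 points (HR 0.80, T = 48: 0.599 to 0.577).

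To put these shares in context, if 1% to 3% of participants used the exception (assumed), that is 950 × 0.01 = 9.5 to 950 × 0.03 = 28.5 people. If each would otherwise have had a counted event and none were recovered, the loss is 9.5/493 = 1.9% to 28.5/493 = 5.8% of events.

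**Direction of bias**

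If a lost event is censored at its event time, the observed HR = true HR × (1 − f_pembrolizumab)/(1 − f_placebo), where f is the fraction of events lost.

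- Equal fractions: 0.75 stays 0.75.
- 5% lost on placebo, 2% on pembrolizumab: 0.75 × 0.98/0.95 = 0.774. A true 1.00 becomes 1.03.
- 2% lost on placebo, 5% on pembrolizumab: 0.75 × 0.95/0.98 = 0.727. A true 1.00 becomes 0.97.

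**The case against.** The strongest reply is that this is a declared, narrow exception to a general rule. It applies only exceptionally. It needs an investigator-called recurrence, instability or rapid deterioration, and Sponsor consultation. Other sections also foresee early ends: 8.11.2.2 routes participants with no further efficacy assessments onward, 8.11.2.3 schedules contacts for those who do not enter Efficacy Follow-up, and 8.2.1.2 lets imaging stop on Sponsor notification. Much of this stands, and it rules out several stronger readings.

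- **Flat contradiction with 8.11.2.2.** A reader might infer one, but an exception that is not cross-referenced is a failure to reconcile. Still, none of the early-end clauses names an unverified recurrence as a reason to stop imaging, so they do not supply the missing link.
- **A small ECOG change opens the route.** ECOG 0 and 1 are both eligible, so 0 to 1 is literally a decline, and the list does not say whether one item is enough. The other conditions must still be met.
- **Losses pull the comparison toward the null because the arm with more recurrences loses more.** More events would be lost there, but equal fractional loss leaves the HR unchanged. The documents give no reason to expect unequal fractions in a particular direction in a double-blind trial.
- **Every such participant is a lost event.** BICR did not verify the recurrence, so some may not be true recurrences. Participants deteriorating rapidly may die soon, and death counts. Pathology counts too.

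Investigator-assessed RFS (9.6.1.1) would expose discrepancies, though it does not recover a BICR event. Table 7, which holds the primary censoring rule and sensitivity analyses, is redacted and may already deal with these participants.

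**Conclusion.** The point holds as an unreconciled and badly worded exception that can cause potentially informative loss or delay of BICR-assessed RFS events. The mechanism rests on the text alone: an exit route from endpoint imaging that depends partly on signs of progression, at a time when verification may need a later scan.

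The size is uncertain and probably modest. The frequency of use is unknown, and the 1% to 3% range is an assumption. The power figures rest on an assumed hazard ratio, alpha and analysis time, and treat every lost event as unrecovered by death or pathology. The direction of any HR bias is not determined. How these participants are censored cannot be judged from the public documents. This does not threaten the trial's validity, but the remedy is cheap and concerns the endpoint that decides success.

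**What to change.** 1. Reword the exception in 8.2.1 so that it applies to study intervention and does not by itself end Efficacy Follow-up. Leave the rule on stopping study intervention as it is.
2. Cross-reference the exception in 8.11.2.2, so that the two sections lead to the same follow-up phase.
3. State that the existing 8.2.1 requirement to send all scans to the imaging CRO continues to apply to these participants, including to standard-of-care scans, until recurrence is verified by BICR or confirmed by pathology. Scans that cannot be done are recorded as missed.
4. Report the number of participants who used the exception, by arm.
5. Unless Table 7 already contains it, add an RFS sensitivity analysis that counts the investigator-called recurrence as an event for these participants.

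The cost is a reworded clause and a cross-reference in an amendment, one count in the report, one added analysis, and a few more missed-scan records. No participant is obliged to undergo a scan they cannot tolerate.
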